5.5. Safety analyses

Adverse events and device deficiencies will be summarized at each study visit based on the safety population for Cohort 1 and Cohort 2 separately. The number and percentage of eyes reported with the ISO specified 3-month cumulative and persistent adverse events will be calculated for Cohort 1 and Cohort 2 separately.

Events will be summarized overall for the HMTIOL Cohort 2 and HMIOL Cohort 2. The corresponding one-sided lower 95% confidence limit will be calculated based on the binomial distribution and compared to the ISO SPE rate.

The number and percentage of eyes reported with HMTIOL-related adverse events during the study will be summarized for HMTIOL Cohort 1, HMTIOL Cohort 2, and HMTIOL-eye Cohort. The two-sided 90% confidence interval of the percentage will also be provided.

The number and percentage of eyes reaching BCDVA 20/40 or better, and worse than 20/40 at each visit will be prepared.

[figure not shown]
Rates for adverse events specified in ISO 11979-7:2014 Annex B for posterior chamber IOLs will be summarized at each visit.

Rates of device-related SSIs and device deficiencies will be summarized as described in 5.1 above.

5.6. Endothelial Cell Counts

The within-eye change and percent change in ECC from preoperative to the 3-month postoperative visit will be calculated for each eye.

*5.7. Other Safety Measures**5.8. Effectiveness Endpoints*

The effectiveness parameters include the following:

- Postoperative MRCYL for eyes implanted with HMTIOL
- Postoperative MRCYL Prediction Error for eyes implanted with HMTIOL
- Postoperative MRSE Prediction Error
- UCDVA by study visit
- BCDVA by study visit
- Rotation of IOL meridian from the day of surgery to 3 months
 - a. Meridian rotation < 10°
 - b. Meridian rotation < 20°
 - c. Meridian rotation < 30°

- Reduction in cylinder power of eye implanted with HMTIOL at 3 months
 - a. Absolute preop magnitude of K (or total corneal cylinder) minus the absolute post op magnitude of MRCYL at the corneal plane
- Percentage reduction in cylindrical power of eye implanted with HMTIOL at 3 months
 - a. Absolute preop magnitude of K (or total corneal cylinder) minus the absolute post op magnitude of MRCYL at the corneal plane expressed as a percentage of the absolute preop magnitude of K (or total corneal cylinder)

5.9. Effectiveness Analyses

All endpoints listed above will be summarized by study visit and cohort as described in section 5.1 based on the Implanted Eye Population. BCDVA will also be summarized based on the Best-case population as suggested by ISO.

5.9.1. BCDVA

[REDACTED] the number and percentage of eyes reaching BCDVA 20/20 or better, 20/25 or better, 20/32 or better, 20/40 or better, and worse than 20/40 at each visit will be prepared for Cohort 1 and Cohort 2 separately.

5.9.2. UCDVA

The proportion of eyes with UCDVA of 20/20 or better, 20/25 or better, 20/32 or better, 20/40 or better, and worse than 20/40 at each visit will be summarized for each Cohort at the preoperative and every postoperative visit.

5.9.3. PREDICTION ERROR (PE)

MRSE prediction error will be calculated at 3 months for each implanted eye as follows:

MRSE PE = Postoperative MRSE adjusted to 6 meters – MRSE TRRE (target residual refractive error)

MRCYL prediction error will be calculated at 3 months for eyes implanted with HMTIOL as follows:

MRCYL PE = Postoperative MRCYL adjusted to 6 meters – MRCYL TRRE (target residual refractive error)

Descriptive statistics for continuous outcomes will be provided for MRSE PE and MRCYL PE at each visit based on Implanted-eye Population. [REDACTED]

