	
Efficacy Endpoints:
 
 
1. Post op MRCYL for eye implanted with HMTIOL
 
2. Post op MRCYL prediction error for eye implanted with HMTIOL
 
3. Post op SEQ Prediction Error
 
4. UCDVA by study visit
 
5. BCDVA by study visit
 
6. Rotation of IOL meridian from the day of surgery to 3 months             
 
a. Meridian rotation < 10°
 
b. Meridian rotation < 20°
 
c. Meridian rotation < 30°
 
 
 
7. Reduction in cylinder power of eye implanted with HMTIOL             
 
a. Absolute preop magnitude of K (or total corneal cylinder) minus the absolute post op magnitude of MRCYL at the corneal plane
 
 
 
8. Percentage reduction in cylindrical power of eye implanted with HMTIOL             
 
a. Absolute preop magnitude of K (or total corneal cylinder) minus the absolute post op magnitude of MRCYL at the corneal plane expressed as a percentage of the absolute preop magnitude of K (or total corneal cylinder)
 
 
 
 
Safety endpoints:
 
 
9. Percent change in ECC at the 3 Month Visit compared to Preoperative Visit
 
10. Preservation of BCDVA
 
11. SSI (other than interoperative optic exchange in Cohort 2)
 
12. Device deficiency
 
13. AEs rates as compared to ISO 11979-7:2014 Annex B SPE tables
 

	

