	
For BCDVA and UCDVA, the number and percentages of eyes with visual acuity of 20/20 or better 20/25 or better, 20/32 or better, 20/40 or better, and worse than 20/40 at each visit will be summarized for Cohort 1 and Cohort 2 separately.
 
The MRSE prediction error will be calculated for each eye (Section 8) and summarized using statistics for continuous variables. The MRCYL prediction error (per cylinder power or vector analysis) will be derived for eye with HMTIOL and summarized using statistics for continuous variables. [REDACTED] The reduction in MRCYL (absolute power) and the percent reduction in cylinder power will be derived for each eyes implanted with HMTIOL. They will be summarized using statistics for continuous variables. [REDACTED]
 
IOL rotation will be derived for each eye from Day 0 (surgery) to postoperative visit. The statistics for continuous variables will be provided. The number and percentage of eyes with rotation of < 10°, < 20°, and < 30° will be calculated [REDACTED]

--	---

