### 7.2 EFFECTIVENESS ENDPOINTS

- 1 and 3 months MRCYL for eyes implanted with HMTIOL
- 1 and 3 months MRCYL prediction error for eyes implanted with HMTIOL
- 1 and 3 months MRCYL prediction error for eyes implanted with HMTIOL per vector analyses
- 1 and 3 months SEQ prediction error
- UCDVA by study visit
  - Percent of eyes that achieve
    - 20/20 or better
    - 20/25 or better
    - 20/32 or better
    - 20/40 or better
    - Worse than 20/40
- BCDVA by study visit
  - Percent of eyes that achieve
    - 20/20 or better
    - 20/25 or better
    - 20/32 or better
    - 20/40 or better
    - Worse than 20/40

- Rotational of IOL meridian at 1 day, 1 week, 1 and 3 months
  - Percent of eyes with rotation < 10°
  - Percent of eyes with rotation < 20°
  - Percent of eyes with rotation < 30°
- Reduction in cylinder power of the eye implanted with HMTIOL (absolute preoperative magnitude of corneal cylinder (K) minus the absolute postoperative magnitude of MRCYL at the corneal plane)
- Percentage reduction in cylindrical power of the eye implanted with HMTIOL (absolute preoperative magnitude of corneal cylinder (K) minus the absolute postoperative magnitude of MRCYL at the corneal plane, expressed as a percentage of the absolute preoperative magnitude of total corneal cylinder (K)).

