#### 8.3.2.3 PREDICTION ERROR (PE)

The MRSE prediction error will be calculated for each treated eye as follows:

MRSE PE = Postoperative MRSE adjusted to 6 meters at 3 months – MRSE TRRE (target residual refractive error)

The MRCYL prediction error will be calculated for eyes implanted with HMTIOL as follows:

MRCYL PE = Postoperative MRCYL adjusted to 6 meters at 3 months – MRCYL TRRE (target residual refractive error)

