1 TITLE PAGE

Protocol Number: ClarVista CP-00002

Medical Specialty: Surgical

Project Name /Number: NA

Sponsor Name & Address: CLARVISTA MEDICAL, INCORPORATED
[name]
[contact]
[contact]Test Article(s) / Product(s): ClarVista HARMONI® Modular Toric Intraocular Lens
System

Statistical Analysis Plan for Protocol CP-00002

A Prospective, Multi-Center Study to Evaluate the Safety and Performance of the Exchangeable ClarVista HARMONI® Modular Toric Intraocular Lens System for the Treatment of Pre-existing Corneal Astigmatism and Aphakia Following Cataract Surgery

Sponsor

ClarVista Medical, Incorporated

[name]

[name]

[contact]

[contact]

Original Version Date

14 August 2017

Table of Contents

1. Purpose.....	3
2. Scope	3
3. Software	3
4. Design and Objectives	3
5. Statistical Analyses	3
6. Sample Size.....	7
7. Analysis Populations.....	7
8. Interim Analyses.....	8
9. Deviations from the Statistical Analysis Plan	9
10. References.....	9

1. Purpose

This is a feasibility study to evaluate the safety and effectiveness of HARMONI® Modular Toric Intraocular Lens System (HMTIOL) in subjects with primary cataract surgery and subjects with HMTIOL intra-operative optic exchange. There are three objectives in this study -

- To demonstrate the safety and effectiveness of the HMTIOL in subjects with pre-existing corneal astigmatism
- To evaluate endothelial cell loss after an intraoperative optic exchange
- To evaluate refractive outcomes and astigmatism correction with the HMTIOL used in the primary surgery

2. Scope

Analyses described here supersede those described in the Investigational Plan.

3. Software

Statistical analyses will be performed with SAS System Software version 9.4 or above (SAS Institute, Cary, N.C.), R version 3.3 or above (R Core Team, <http://www.R-project.org>), or other validated statistical software package.

4. Design and Objectives

All subjects will be bilaterally implanted based on the amount of pre-existing corneal astigmatism and followed for a period of 3-months post-implantation. The eye with the higher corneal astigmatism will be assigned to Cohort 1 and will undergo cataract surgery receiving HMTIOL. The contralateral eye will be assigned to Cohort 2, undergo cataract surgery, receive a HMTIOL or HMIOL (toric or non-toric optic, respectively), and undergo intraoperative exchange.

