**8. Interim Analyses**

There are no plans for formal interim analyses for the purposes of study modification or possible early termination. Any interim analyses will be administrative in nature and results will not be distributed to Investigators or subjects to prevent bias from exposure to accruing study results.

SAP CP-00002

[figure not shown]
ClarVista Medical, Inc.

9. Deviations from the Statistical Analysis Plan

Any deviations from the Statistical Analysis Plan will be noted and described with appropriate statistical and clinical rationale as needed. Discrepancies from the Investigational Plan are noted. The primary change is the use of a paired t-test instead of a two-sample t-test to test the primary hypothesis. This change more appropriately accounts for within-patient correlation in ECC. A secondary change was the use of "ECC" rather than "ECL" in Sections 6 and 7 above. ECL is defined in the protocol as follows: "a negative ECC percent change represents an ECC percent loss (ECL)." Since a comparison of 3-month to Pre-operative data may not always result in a measurable loss (e.g., due to measurement error of instrumentation combined with minimal actual ECC loss), ECC is determined to be a more appropriate term.

10. References

1. ISO 11979-7:2014 Ophthalmic implants — Intraocular lenses — Part 7: Clinical investigations.

Alcon - Business Use Only

Document: TDOC-0055985

Status: Effective

Effective Date: 24-Apr-2019

Version: 1.0; CURRENT; Most-Recent; Effective

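### Protocol 7.2 names a vector MRCYL prediction error as an endpoint, but the visible SAP neither lists nor defines one and gives only a cylinder difference without axis

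*SAP*

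**What the plan says.** **Protocol.** Section 7.2 has one bullet for the MRCYL prediction error at 1 and 3 months and a separate bullet reading "1 and 3 months MRCYL prediction error for eyes implanted with HMTIOL per vector analyses". Other parts of the protocol are weaker:
- The synopsis endpoint list has one entry, "Post op MRCYL prediction error for eye implanted with HMTIOL".
- The synopsis paragraph on planned analyses allows either form: "The MRCYL prediction error (per cylinder power or vector analysis) will be derived for eye with HMTIOL".
- Section 8.3.2.3 gives only the scalar formula, "MRCYL PE = Postoperative MRCYL adjusted to 6 meters at 3 months – MRCYL TRRE (target residual refractive error").

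**SAP.** Section 2 states: "Analyses described here supersede those described in the Investigational Plan". The 5.8 list has one entry, "Postoperative MRCYL Prediction Error for eyes implanted with HMTIOL", and 5.9 says that the endpoints in that list are the ones summarised. Section 5.9.3 defines "MRCYL PE = Postoperative MRCYL adjusted to 6 meters – MRCYL TRRE (target residual refractive error"), followed by continuous-variable summaries and then a redacted block. Section 9 says "Discrepancies from the Investigational Plan are noted". It describes a primary change (paired instead of two-sample t-test) and a secondary one (ECC instead of ECL), and does not mention the vector analysis.

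**The concern.** Cylinder has a size and an axis. A difference of two cylinder powers ignores the axis, so an eye that ends with the planned amount of cylinder at the wrong axis scores an error of zero. Evaluating astigmatism correction with the toric lens is a specific objective (protocol 2.0), and the prediction error is the planned measure in dioptres of how closely the achieved cylinder matches the target.

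The other SAP analyses do not fill the gap. Sections 5.9.4 and 5.9.5 measure the position of the lens meridian in degrees, and a well-placed lens can still leave refractive error. Section 5.9.6 uses magnitudes only. If the scalar form were the only one reported, a reader could take the correction to be more accurate than it is and could not see the direction of any systematic error.

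**Working it through.** The documents give no numerical result for this endpoint, so there is no figure to reproduce. The check has two parts.

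**1. Which sections name the vector form**

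| Place | Scalar | Vector |
|---|---|---|
| Protocol synopsis, endpoint list | one entry, form not stated | not named |
| Protocol synopsis, planned analyses | either form | either form |
| Protocol 7.2 | yes | yes, own bullet |
| Protocol 8.3.2.3 | formula | no visible formula |
| SAP 5.8 | one entry, form not stated | not named |
| SAP 5.9.3 | formula | no visible formula; redacted block follows |
| SAP 9 | – | not mentioned |

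**2. What the scalar form loses**

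Let T be the target and P the postoperative residual cylinder, as double-angle vectors.
- Scalar PE = |P| − |T|, taking MRCYL as a positive magnitude. Neither formula states the sign convention.
- Vector PE = |P − T|.
- By the reverse triangle inequality, | |P| − |T| | ≤ |P − T|. The absolute scalar error therefore never exceeds the vector error.
- If |T| = 0, both equal |P|. There is no gap in size, but the direction of P is not reported.
- If |P| = |T| = M and the axes differ by t, the scalar PE is 0 and the vector PE is 2M sin t. For M = 0.50 D and t = 30°, this is 2 × 0.50 × 0.5 = 0.50 D. For M = 0.25 D and t = 10°, it is 2 × 0.25 × 0.174 = 0.09 D.

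**Illustration of the average gap**

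From the documents (protocol 3.2.1): corneal cylinder 0.75 to 2.50 D; toric steps 1.50, 2.25 and 3.00 D at the lens plane.

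Assumed, because the documents do not give them: corneal cylinder uniform over that range, ratio of corneal-plane to lens-plane power 0.65 to 0.80, no surgically induced astigmatism, and independent normal errors with SD 0.30 D in each component. Simulation used 1,000,000 draws per setting.

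With no systematic error, the mean vector error is SD × √(π/2) = 0.30 × 1.2533 = 0.376 D, whatever the target. The mean scalar PE depends on the lens-selection rule, which the documents do not state:

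| Lens rule (assumed) | No systematic error | 0.30 D overcorrection | 0.30 D undercorrection |
|---|---|---|---|
| Nearest lens | 0.25–0.26 D | 0.29–0.36 D | 0.30–0.36 D |
| Largest lens not exceeding the cylinder, otherwise the smallest | 0.20–0.22 D | 0.18–0.21 D | 0.34–0.38 D |

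In both systematic-error columns the mean vector error is 0.465 D, and the mean along the planned axis is 0.30 D with opposite signs. Under the nearest-lens rule, the scalar mean rises by a similar amount in either direction. Under the other rule it responds to undercorrection but barely registers overcorrection.

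Under the nearest-lens rule with no systematic error, an SD of 0.20 D gives a mean scalar PE of 0.14–0.15 D against a vector mean of 0.25 D. An SD of 0.40 D gives 0.37–0.38 D against 0.50 D.

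**The case against.** **Redaction.** A reader might infer that the SAP drops the vector endpoint. The documents do not support that. Redacted text directly follows the 5.9.3 summary sentence and could define the vector method. Nor does the lack of a redaction mark in 5.8 settle the matter, because nearby SAP text has unmarked gaps: heading 5.7 has no body. The entry in 5.8 is also general enough to cover both forms. This objection stands, and it limits the point to the visible text.

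**The protocol itself.** SAP 5.8 closely follows the synopsis list, and the 5.9.3 formula is that of protocol 8.3.2.3. The synopsis analysis paragraph would be satisfied by the scalar form alone. Only one bullet in 7.2 differs. This also stands, so the inconsistency is not the SAP's alone. An SAP that takes precedence is still the place to settle it.

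**Section 9.** A reader might infer that the change log failed. Section 9 does not claim to be complete, and other visible differences, such as the added 5° category for rotation, are not logged either. Silence there is not strong evidence of an unrecorded change.

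**The numbers.** A reader might infer that the scalar always understates the error, or that it can never tell overcorrection from undercorrection. Neither holds in general. At zero target the magnitudes are equal, and under the second lens rule the scalar mean differs clearly between the two directions. The sizes shown rest on assumed inputs.

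**Conclusion.** The mismatch holds for the visible text: an endpoint that protocol 7.2 names separately has no entry of its own and no visible definition in the SAP. The inequality between the two forms is exact, but a gap in size arises only where the target residual cylinder is not zero. At an assumed SD of 0.30 D, the mean vector error of 0.38 D exceeds the mean scalar PE by about 0.12 to 0.18 D (0.38 − 0.26 to 0.38 − 0.20) across the two lens rules. How well the scalar shows systematic over- or undercorrection depends on a lens rule that the documents do not state.

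Minor. The study is a feasibility study, protocol 8.3.2 describes effectiveness outcomes other than BCDVA as exploratory, and the consequence is limited to how a descriptive result is read.

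**What to change.** - In SAP 5.8 and 5.9.3, list and define the vector MRCYL prediction error at 1 and 3 months, alongside the existing scalar one. One suitable definition is the double-angle difference between achieved and target residual cylinder at the corneal plane. Report its mean magnitude, and its centroid with each eye referred to its own planned axis so that eyes with perpendicular axes do not cancel. Protocol 7.2 asks only for vector analyses, so this particular definition is a suggestion.
- If redacted text already defines the vector form, name it in 5.8. If it was left out on purpose, record that in section 9.
- Make the synopsis (endpoint list and planned analyses), protocol 7.2 and protocol 8.3.2.3 agree.

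**Cost.** SAP wording and some programming, with no new visit: manifest refraction is already scheduled at 1 and 3 months. The 5.9.3 formula already needs the target cylinder. The added item is the axis of the target residual, to be taken from the preoperative toric calculation that the sponsor already reviews (protocol Appendix A). The lens axis recorded at surgery is not the same quantity. Reported accuracy may look less favourable than with the scalar form alone.

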5.9.4. MISALIGNMENT OF IOL MERIDIAN

The final rotational meridian of the IOL will be compared to the planned position. The absolute value of rotation will be described by mean, median, and maximum values. The signed value of rotation will be described by mean, SD, minimum and maximum values. The number and percentage of eyes with deviation $\leq 5^\circ$, $< 10^\circ$, $< 20^\circ$, and $< 30^\circ$ from the planned meridian will be calculated.

5.9.5. ROTATION OF IOL MERIDIAN

The rotation of IOL meridian will be calculated for each eye from Day 0 to every postoperative visit.

Descriptive statistics for continuous variables will be used to summarize the rotation angle at each visit.

The absolute value of rotation will be described by mean, median, and maximum values. The signed value of rotation will be described by mean, SD, minimum and maximum values. The number and percentage of eyes with rotation $\leq 5^\circ$, $< 10^\circ$, $< 20^\circ$, and $< 30^\circ$ will be calculated at each visit.

Axis shift by 5° increments will also be stratified for each preoperative corneal cylinder diopter bin.

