### 3.3.2 DAY 0 VISIT (CATARACT SURGERY AND IOL IMPLANTATION)

Record any changes in concomitant medications and medical history, prepare the subject for surgery in the study eye (see Surgical Procedure Guide), and re-review inclusion/exclusion criteria to ensure subject still qualifies to participate.

All subjects with an odd subject number will have their Cohort 1 eyes done first. All subjects with and even subject number will have their Cohort 2 eyes done first.

The Investigator will carry out the surgical procedure and HMTIOL or HMIOL implantation as specified in the Surgical Procedure Manual and the following details will be captured in both Source Documents and eCRFs:

- Date of surgery
- Operative eye
- Cohort 1 or Cohort 2
- Incision location and size
- Ophthalmic Viscoelastic Device (OVD) used
- All medication used pre-, intra-, and post-operatively (ophthalmic and systemic)
- Model, serial number, and diopter of HMTIOL or HMIOL implant components
- Toric IOL power and axis orientation (for HMTIOL)
- IOL injection device

Once the subject is confirmed stable post-surgery, provide IRB / EC approved post-operative instructions and discharge.

Record any AEs, adverse device effects (ADEs), unexpected adverse device effects (UADEs), or device deficiencies (DD) (see Sections 6.1.1, 6.1.2, 6.1.3, or 6.1.4 respectively) observed pre-, intra-, or post-operatively.

In the event the subject is not implanted with the HMTIOL or HMIOL, the surgeon will provide the best care option to the patient, including implanting a commercially available IOL. In the event the optic cannot be exchanged, the surgeon will provide the best care option to the patient, including keeping the existing optic.

In the event the subject is not implanted with an HMTIOL or HMIOL device due to an intra-operative complication, the subject will be discontinued (see Section 4.5).

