**8.3.2.4        *ROTATION OF IOL MERIDIAN***

The rotation of IOL meridian will be calculated for each eye from Day 0 to every postoperative visit. The descriptive statistics for continuous variables will be used to summarize the rotation angle at each visit for Cohort 1 and Cohort 2 separately. Additionally, the number and percentage of eyes with rotation < 10°, < 20°, and < 30° will be calculated at each visit for Cohort 1 and Cohort 2 separately. [REDACTED]

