7.1.2. IMPLANTED-EYE POPULATION

The Implanted-Eye Population consists of eyes with successful HMTIOL or HMIOL implantations during surgeries. Since it is important to evaluate HMTIOL or HMIOL's effect on the study eyes, the assessment of ECC, slit lamp examination, intraocular pressure (IOP), and dilated fundus examination (DFE) will be based on the implanted-eye population. It should be noted that the ECC comparison between Cohort 1 and Cohort 2 of this study will be based on the subjects with successful implants in both eyes and have available ECC data at 3 months.

Additionally, the UCDVA, BCDVA, prediction error, and meridian rotation will be evaluated based on the implanted-eye population.

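### IOL rotation is not limited to toric eyes in the readable text, so the Cohort 2 rotation summaries can mix HMTIOL and HMIOL eyes

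*SAP*

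**What the plan says.** **Rotation.** SAP 5.9.5: "The rotation of IOL meridian will be calculated for each eye from Day 0 to every postoperative visit". The section then asks for descriptive statistics, the share of eyes under several angle limits at each visit, and axis shift in 5° steps within bins of preoperative corneal cylinder. It names no lens type. Protocol 8.3.2.4 also uses each eye, and gives results for each of the two cohorts on its own ("the number and percentage of eyes with rotation < 10°, < 20°, and < 30° will be calculated at each visit for Cohort 1 and", where the sentence goes on to name the second cohort); a redaction follows.

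**Grouping and population.** SAP 5.9: "All endpoints listed above will be summarized by study visit and cohort as described in section 5.1 based on the Implanted Eye Population". Rotation and UCDVA are on the SAP 5.8 list to which this refers. SAP 7.1.2: "The Implanted-Eye Population consists of eyes with successful HMTIOL or HMIOL implantations during surgeries".

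**Lenses.** Cohort 1 receives HMTIOL. Under SAP 4, Cohort 2 eyes "receive a HMTIOL or HMIOL (toric or non-toric optic, respectively), and undergo intraoperative exchange".

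**Misalignment.** SAP 5.9.4: "The final rotational meridian of the IOL will be compared to the planned position". It names neither the eyes nor the cohorts, and misalignment is not on the 5.8 list.

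**Data capture.** The Day 0 list in Protocol 3.3.2 includes "Toric IOL power and axis orientation (for HMTIOL"), and the second-eye list in 3.3.3 likewise ties axis orientation to toric lenses. Appendix A schedules rotational-stability photographs for both cohorts, at surgery and at every postoperative visit, with no lens restriction.

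**The concern.** The plan separates toric from non-toric eyes for other endpoints. SAP 5.8 limits MRCYL, and SAP 5.9.3 limits MRCYL prediction error, to HMTIOL eyes. SAP 5.9.6 does the same for cylinder reduction, and Protocol 8.3.2.5 reports that endpoint for Cohort 1 and for the HMTIOL eyes of Cohort 2. SAP 5.5 uses HMTIOL Cohort 1, HMTIOL Cohort 2, HMIOL Cohort 2 and an all-HMTIOL group for adverse events. Rotation, the endpoint most specific to a toric lens, has no such limit.

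The protocol's Introduction puts the loss of toric correction at 3% per degree in one place and 3.3% in another. That gives rotation a refractive meaning only for a toric optic. SAP 1 says the study is to evaluate HMTIOL both in primary surgery and after intraoperative optic exchange. Only the toric eyes of Cohort 2 show how the toric lens holds its position after exchange, and a Cohort 2 figure that includes HMIOL eyes does not isolate them.

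UCDVA raises a smaller question. It is summarised per cohort, so the Cohort 2 figure may combine eyes given a toric correction with eyes given none.

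**Working it through.** The plan gives no figure to reproduce. The check is which eyes can enter the tables, followed by an illustration.

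**1. Can HMIOL eyes be in Cohort 2?** Yes. Inclusion criterion 4 requires qualifying astigmatism in at least one eye, and Cohort 2 takes the eye with the lower astigmatism. The documents do not fix the split.

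**2. Do the rules exclude them from rotation?** Not in the readable text. SAP 5.9.5 covers each eye, SAP 5.9 groups by cohort, and the Implanted-Eye Population holds both lenses.

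**3. What happens to an HMIOL eye in practice?** The documents do not say whether the HMIOL carries a mark from which rotation can be read. There are two cases:
- *It is read*, because the photographs are scheduled. It then enters the percentages and the axis-shift table.
- *It is not read*, because no axis is recorded at surgery. SAP 5.1 then drops it from the numerator and denominator of the percentages, but counts it as not reported in the continuous summary. An eye to which the endpoint does not apply then looks like missing data.

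**4. Illustration for the first case.** From the documents: N = 32 Cohort 2 eyes (planned enrolment, SAP 6). Assumed: k non-toric eyes, 90% of toric eyes rotating less than 10°, and a non-toric rate p between 50% and 100%.

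Pooled share = [(32 − k) × 0.90 + k × p] / 32

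| k | p = 50% | p = 100% | Toric eyes |
|---|---|---|---|
| 8 | (21.6 + 4)/32 = 80.0% | (21.6 + 8)/32 = 92.5% | 24 |
| 16 | (14.4 + 8)/32 = 70.0% | (14.4 + 16)/32 = 95.0% | 16 |
| 24 | (7.2 + 12)/32 = 60.0% | (7.2 + 24)/32 = 97.5% | 8 |

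The toric-only figure is 90% in every row. Pooling can move it up or down. With k = 0 there is no effect.

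In counts, with k = 16 and two toric eyes rotated 10° or more:
- toric eyes only: 2/16 = 12.5%;
- pooled with 16 stable HMIOL eyes: 2/32 = 6.3%;
- pooled when half of the HMIOL eyes rotated: (2 + 8)/32 = 31.3%;
- HMIOL eyes not read: 2/16 = 12.5% again.

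**5. UCDVA.** With assumed rates of 80% (toric) and 60% (non-toric) for 20/25 or better, the pooled figure is (24 × 0.80 + 8 × 0.60)/32 = 75% for k = 8, 70% for k = 16, and (8 × 0.80 + 24 × 0.60)/32 = 65% for k = 24. Here the pooled result changes with the lens mix alone.

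**The case against.** Several points on the other side stand.

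- A reader might infer that the effectiveness results as a whole fail to describe the toric lens. They do not: Cohort 1 is entirely HMTIOL and is reported separately. It also serves the refractive objective, which concerns HMTIOL in primary surgery.
- A reader might infer that misalignment is also summarised for every eye by cohort. SAP 5.9.4 says neither. A comparison with a planned position largely restricts itself to eyes that have a planned axis; what is missing is a statement of the population.
- A reader might infer that dilution of the Cohort 2 rotation rate is certain, and that it flatters the lens. The SAP 5.1 rule on eyes without results could remove every HMIOL eye from the percentages, and pooling could move them either way.
- UCDVA is a valid measure in an HMIOL eye, and no comparison of UCDVA between cohorts is visible. This supports an extra breakdown, not an exclusion.
- Protocol 8.3.2 calls effectiveness outcomes other than BCDVA exploratory, and this is a feasibility study.
- If HMIOL eyes fall in the low corneal-cylinder bins, the binned axis-shift table already separates them in part.
- A split may exist in text that cannot be read. Redactions follow the rotation text in the protocol synopsis and in 8.3.2.4, and one opens 8.3.2.2 on UCDVA. A sentence in Protocol 8.3 on separating eye data breaks off. The relevant SAP sections show no redaction mark, but unmarked gaps are possible: SAP 5.7 is a heading without text, and the paired t-test mentioned in SAP 9 does not appear in SAP 5.6.

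These points narrow the concern but do not remove it. The readable rule for rotation is broader than the rules beside it, and either treatment of HMIOL eyes leaves the Cohort 2 table open to misreading.

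**Conclusion.** The point holds for Cohort 2 rotation, in the readable text. Its rotation percentages and axis-shift table can combine toric with non-toric eyes, or count non-toric eyes as not reported. Cohort 1's own summaries are unaffected. The misalignment section needs its population stated, and the Cohort 2 UCDVA summary would be clearer by lens type.

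The size and direction of any effect are unknown. They depend on the number of HMIOL eyes, on whether those eyes can be read for rotation, and on how they behave; the documents give none of these. The 60.0% to 97.5% range around an assumed toric rate of 90% illustrates sensitivity and is not an estimate. The conclusion also assumes that the unreadable text holds no split. This is an inexpensive improvement to a descriptive analysis, not a flaw that undermines the study.

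**What to change.** - **SAP 5.9.5 and Protocol 8.3.2.4:** report rotation and the axis-shift table for HMTIOL eyes, in three groups: Cohort 1, HMTIOL eyes in Cohort 2, and all HMTIOL eyes. Show any HMIOL readings separately, and do not count unread HMIOL eyes as missing rotation results.
- **SAP 5.9.4:** state that misalignment from the planned meridian applies to HMTIOL eyes.
- **SAP 5.9.2:** keep the UCDVA summary by cohort and add Cohort 2 by lens type, using the HMTIOL Cohort 2 and HMIOL Cohort 2 groups already in SAP 5.5.

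If the redacted text already does this, only the wording of these sections needs to be brought into line. The cost is SAP wording and extra table columns, with no new data. Cohort 2 denominators become smaller: 24, 16 or 8 toric eyes instead of 32 under the splits assumed above.
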